9 CONFOUNDING

Relative hypotension associated with deep anaesthesia is suspected to be a confounding factor that may be the explanation for observed mortality difference in the published evidence to date. The BALANCED study design has attempted to mitigate these effects (via the use of vasopressors and inotropes) but achieved MAP may still confound the comparison between randomised groups. A multivariate analysis of 1 year mortality will be undertaken using Cox proportional hazards regression in which randomised group, study-centre-group, the use of vasopressors/inotropes and achieved MAP are included as covariates.

9.1 Additional analyses

- Additional analyses of efficacy endpoints will be undertaken using the PP participant population and including the intermediate BIS group 40 to 45.
- Efficacy endpoints will be summarised by randomized group within categories for age, ASA, surgery type, centre, use of vasopressors/inotropes and anesthetic duration (quartiles). These results will be summarized using forest plots and the consistency of the difference between randomised groups tested using interaction terms within Cox-regression and general linear models as appropriate.
- Multi-variate analyses will be used to explore the independent and combined effects of randomised treatment, age, ASA, surgery type, study centre-groups, anesthetic duration, the use of inotropes, achieved MAP and achieved BIS group on the efficacy endpoints.

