4 GENERAL ANALYSIS DEFINITIONS

4.1 Treatment Allocation

Once all entry details are recorded and eligibility confirmed, randomisation will be performed by contacting the automated on-line randomisation service with back-up phone service. Assignment to one of the two groups will be stratified by collaborating centre-group and a unique study number assigned.

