4.3 Participant Populations

4.3.1 Intention-To-Treat Population (ITT)

The primary and secondary outcomes will initially be analysed using the full analysis set population i.e. the intention-to-treat population which includes all randomised patients undergoing induction of general anaesthesia for surgery. Sensitivity analyses will also be undertaken, as appropriate. In these analyses missing outcome data will be assigned a poor outcome.

In the event that patients withdraw (discontinue participation in the study or are lost to follow-up), information on their survival and secondary endpoint status at the time they are withdrawn will be included in the relevant endpoint analysis.

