6 PARTICIPANT DISPOSITION

A flowchart will be produced showing the flow of participants throughout the study. The numbers of participants approached, screened and consented will be summarised. Those who are screened and consented but not randomised will also be summarised.

Any participants who are randomised but do not have surgery will be individually listed with explanation, by randomised group.

Any patients inappropriately randomised (subsequent to randomisation are found to violate inclusion/exclusion criteria) will also be individually listed with their inclusion or exclusion violations.

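### Section 9.1 uses vasopressor/inotrope use as a subgroup factor with interaction tests, although it is determined after randomisation and can depend on the allocated BIS target

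*Combined protocol and SAP*

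**What the plan says.** Section 9.1 (Additional analyses) names six subgroup factors in one sentence: "Efficacy endpoints will be summarised by randomized group within categories for age, ASA, surgery type, centre, use of vasopressors/inotropes and anesthetic duration (quartiles". The results go into forest plots, and consistency of the treatment difference is to be "tested using interaction terms within Cox-regression and general linear models as appropriate". The six factors are treated alike, and no caveat separates those fixed before allocation from those arising afterwards.

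The order of events comes from three other places:

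- Section 4.1: "Once all entry details are recorded and eligibility confirmed, randomisation will be performed by contacting the automated on-line randomisation service".
- Section 4.3.1 defines the ITT set as "all randomised patients undergoing induction of general anaesthesia for surgery", so induction follows randomisation.
- Section 6: "Any participants who are randomised but do not have surgery will be individually listed with explanation, by randomised group". Randomisation therefore also precedes surgery.

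Section 9 supplies the link between allocation and vasopressor use: "Relative hypotension associated with deep anaesthesia is suspected to be a confounding factor", and the design "has attempted to mitigate these effects (via the use of vasopressors and inotropes".

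**The concern.** A subgroup analysis keeps the benefit of randomisation only if membership is settled before allocation, or at least cannot be changed by it. Age, ASA, surgery type and centre meet that condition. Vasopressor/inotrope use does not meet it on the plan's own reasoning: the target influences blood pressure, and blood pressure prompts the drugs. If use also tracks patient risk, users in one arm may be a different kind of patient from users in the other, and likewise for non-users.

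The vasopressor row is the one most likely to be read as evidence on mechanism, because Section 9 names hypotension as a suspected explanation for the published mortality difference. In a forest plot beside four valid baseline factors, with an interaction p-value, nothing would tell the reader that it is a different kind of comparison.

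**Working it through.** **Plan's own figure (background only).** Section 4.2 gives 3250 per group for 10% against 8%, power 0.8 and alpha 0.049. With n = [z(1−α/2)·√(2p̄q̄) + z(power)·√(p₁q₁ + p₂q₂)]² / (p₁ − p₂)²:

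(1.9686 × 0.4047 + 0.8416 × 0.4045)² / 0.0004 ≈ 3233 per group.

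Power at 3250 is 80.2%. The figure reproduces, and the point does not depend on it. The design effect as an odds ratio is (0.08/0.92)/(0.10/0.90) = 0.78, a useful yardstick.

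**Step 1: timing of each factor.**

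| Factor in Section 9.1 | Fixed before randomisation? | Path from allocation in the documents? |
|---|---|---|
| Age, ASA, surgery type, centre | Yes | None |
| Vasopressor/inotrope use | No | Yes (Section 9) |
| Anaesthetic duration, quartiles | No | None stated |

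**Step 2: how large could the bias be?** The documents give no rate of use, no difference in use by arm and no relation of use to risk. Everything below is assumed except overall mortality of 10% (Section 4.2). The target has no effect on death in anyone, so every true odds ratio (OR) is 1.00. The plan would use Cox models for the interaction; odds ratios at one year serve here as illustration.

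*Model A, two risk classes.* 30% of patients are frail with 20% mortality and the rest have 5.71%, so overall mortality is 0.3 × 0.20 + 0.7 × 0.0571 = 0.100. If a fraction v₁ of frail patients and v₀ of the others receive the drugs, mortality among users is

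(0.3·v₁·0.20 + 0.7·v₀·0.0571) / (0.3·v₁ + 0.7·v₀),

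with 1 − v in place of v for non-users.

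The extreme case has use of 90% frail/80% others at BIS 35, and 90%/40% at BIS 50:

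- Users, BIS 35: (0.0540 + 0.0320)/0.83 = 0.1036. BIS 50: (0.0540 + 0.0160)/0.55 = 0.1273. OR = 1.26.
- Non-users, BIS 35: (0.0060 + 0.0080)/0.17 = 0.0823. BIS 50: (0.0060 + 0.0240)/0.45 = 0.0666. OR = 0.80.

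*Model B, continuous frailty.* Standard normal frailty raises the log-odds of use by 0.9 per SD and of death by 0.8 per SD. BIS 35 raises the log-odds of use by a set amount. Stratum mortalities come from numerical integration over frailty.

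Results, all as OR for BIS 50 against BIS 35:

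| Assumed use | Users | Non-users |
|---|---|---|
| A: equal in both arms (90%/60%) | 1.00 | 1.00 |
| B: arm log-OR 0 | 1.00 | 1.00 |
| B: arm log-OR 0.2, 30–50% use at BIS 50 | about 1.02 | about 1.02–1.03 |
| A: 85%/65% at BIS 35, 80%/55% at BIS 50 | 1.04 | 1.01 |
| B: arm log-OR 0.7, 30% use at BIS 50 (44% at BIS 35) | 1.09 | 1.09 |
| B: arm log-OR 0.7, 50% use at BIS 50 (65% at BIS 35) | 1.08 | 1.09 |
| A: 90%/70% at BIS 35, 80%/40% at BIS 50 | 1.16 | 1.00 |
| A: 90%/80% at BIS 35, 90%/40% at BIS 50 | 1.26 | 0.80 |

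The two log-OR 0.7 rows correspond to about 0.92 in both strata when expressed as BIS 35 against BIS 50.

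**Step 3: would an interaction test pick it up?** With 3250 per arm, 50% use and 9% mortality in every cell, each cell has 1625 patients and the SE of the log ratio of ORs is √{4 × [1/(1625 × 0.09) + 1/(1625 × 0.91)]} = 0.17. In Model B at log-OR 0.7 and 50% use, the stratum ORs differ by a ratio of about 1.01 (log 0.01), under 0.1 SE: a shared shift with practically no interaction. In the extreme case the ratio is 1.26/0.80 ≈ 1.6 (log 0.46). From that case's own cell sizes and risks, the SE is √(0.0040 + 0.0050 + 0.0240 + 0.0110) = 0.21, so the false interaction is about 2.2 SE.

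**The case against.** The strongest reply is that a reader might infer from the design flaw that the interaction test will manufacture effect modification. In general it will not. Under the smooth model with a sizeable difference in use, both strata shift together and the interaction stays near nil; the overall ITT result beside them would show that something is amiss. A large false interaction needs a particular pattern, with use doubled in lower-risk patients and unchanged in frail ones. Nothing in the documents says that this pattern occurs, or that users under lighter anaesthesia are the sicker ones. This stands, and is why the size is given as a range starting at nil. It does not remove the point: a shared shift in both strata is still bias in the contrasts that the forest plot displays.

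Second, a reader might treat anaesthetic duration as equally compromised. The documents do not support that. Being measured after randomisation is not the same as being affected by it, and no section says that depth alters duration. Section 5 even lists surgical duration with the baseline characteristics. If allocation leaves duration unchanged, bias should be small. This stands too.

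Third, these are additional analyses. The Mantel-Haenszel test of the primary endpoint in the ITT population, the sample size and the Holm-Bonferroni procedure for secondary endpoints do not use the subgroup factors. That is correct and sets the severity. Secondary status does not, however, turn a non-randomised contrast into a randomised one.

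**Conclusion.** The point holds for vasopressor/inotrope use. It arises after randomisation, Section 9 provides a route from the allocated target to its use, and Section 9.1 presents it without distinction beside valid baseline factors. Under no true effect and assumed inputs, the stratum odds ratios run from 1.00, through about 0.92 in both strata for BIS 35 against BIS 50, to 1.26 and 0.80 for BIS 50 against BIS 35 in an extreme pattern. That last case is of the same order as the design odds ratio of 0.78. Where the trial would fall cannot be told from the documents.

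For anaesthetic duration the point is a caution resting on timing alone. The documents do not support a claim that either row is bound to mislead, or that the primary result is at risk. Severity is minor.

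**What to change.** Amend Section 9.1 in three respects:

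1. Limit the subgroup interaction tests and the main forest plot to factors fixed before randomisation: age, ASA, surgery type and centre.
2. Tabulate vasopressor/inotrope use and anaesthetic duration by randomised group, so that readers can see whether either differs by arm.
3. If outcomes are still shown within these two factors, put them in a separate descriptive display, without interaction tests, labelled as non-randomised comparisons.

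No new subgroup factors are needed. The cost is a wording change, which Section 13 allows as an SAP amendment before database lock, one added table, and the loss of the exploratory interaction tests on two factors.

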10 SAFETY ANALYSES

Safety analyses will be performed using the safety population as defined above. Adverse events and serious adverse events will be tabled as frequencies and percentages within Common Terminology Criteria for Adverse Events (CTCAE) preferred term and system organ class classifications by randomised group, severity class and relatedness to randomised treatment. Additionally, the incidence of adverse events (events/p-year) will be calculated and summarised by randomised group.

11 PROTOCOL VIOLATIONS

All protocol violations and deviations will be individually listed by randomised group.

12 MISSING DATA

In the event that a patient withdraws (discontinues the study or is lost to follow-up) from the study, information on their survival and secondary endpoint status at the time they are withdrawn will be included in the relevant endpoint analysis. Sensitivity analyses will also be undertaken with those missing outcome event data will be assigned a poor outcome. There will be no imputation of the ICU stay, hospital stay, days disability-free and alive within one-year post-surgery and WHODAS data at 30 days and 1 year.

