3.3 Secondary Objectives

The secondary efficacy objective is:

- To compare secondary efficacy/safety endpoints to one-year between randomised BIS target groups 50 and 35.

The secondary endpoints are:

1. **MI:** According to the 3rd Universal Definition (Thygesen K, Alpert JS, Jaffe AS, et al. Third universal definition of myocardial infarction. Circulation 2012;126:2020-35.), defined by either of:
 - A typical rise of troponin OR a typical fall of an elevated troponin OR a rapid rise and fall of CK-MB, PLUS one of the following: i) ischaemic symptoms, ii) pathological Q waves, iii) ECG changes indicative of ischaemia, iv) coronary artery intervention, and/or v) new or presumed new wall motion abnormality on echo or mibi scan; OR
 - Autopsy findings of MI
2. **Cardiac arrest:** Defined as a successful resuscitation from either documented or presumed ventricular fibrillation or sustained ventricular tachycardia or asystole
3. **Pulmonary embolism:** high probability VQ scan or documented on pulmonary angiogram or spiral CT, or at autopsy
4. **Stroke:** cerebral infarction or haemorrhage on CT or MRI scan, or new neurological signs (paralysis, weakness or speech difficulties) lasting more than 24 hours or leading to earlier death
5. **Sepsis:** using Centers for Disease Control and Prevention with National Healthcare Safety Network criteria: - SIRS plus infection (positive blood culture or purulence from any site)
6. **Surgical site infection:** if associated with purulent discharge and/or a positive microbial culture
7. **MI, cardiac arrest, PE and stroke:** the composite of secondary cardiac endpoints 1 to 4.
8. **Total ICU stay:** including initial ICU admission and readmission time
9. **Hospital stay:** from the start (date, time) of surgery until actual hospital discharge.

10. **Awareness:** Questioning for evidence of awareness under anaesthetic using the modified Brice questionnaire administered once in hospital, preferably on the day following surgery, and again on day 30.
11. **WHODAS score:** pre-operative, day 30 and 1 year
12. **Disability free survival:** disability-free survival up to 1 year: survival and freedom from new-onset disability, the latter defined as a 4-point or greater increase in the WHODAS score. Disability will be assessed by the participant, but if unable then we will use the proxy's report. The date of onset of new disability will be recorded.

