4.2 Sample size calculation

One year all-cause mortality is expected to be ~10% based on the findings of Leslie et al. and Gurman et al. The relative risk reduction in mortality in the BIS=50 group is expected to be 20%. A power analysis using $p_1=0.10$ and $p_2=0.08$ indicates that $N=3250$ patients are required in each group, $1-\beta=0.8$, $\alpha=0.049$. The alpha level is reduced to allow for the single interim analysis.

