8 EFFICACY ANALYSES

8.1 Primary endpoint analyses:

The primary endpoint analysis will compare the primary endpoint, one-year mortality in the intention-to-treat population, using a Mantel-Haenszel Chi-square test, stratified by study-centre groups. The pooled estimate of the odds ratio and 95% confidence interval from this analysis will be used to summarise the statistical comparison.

Supportive analysis of the primary endpoint will compare randomised groups using a stratified log-rank test with results summarised using Kaplan-Meier curves and hazard ratios in which withdrawn participants will be censored at the last date that they are confirmed to be event-free.

A two-tailed p-value < 0.049 will be taken to indicate statistical significance. The primary endpoint will be analysed using the full analysis set i.e. using those individuals who have confirmed outcome status, with groups designated as randomised on the intention-to-treat basis. Sensitivity analyses will also be undertaken with those missing outcome data assigned a poor outcome.

8.2 Secondary efficacy analyses:

The differences between randomised groups will be analysed using stratified Mantel-Haenszel Chi-square tests, stratified by study-centre group and general linear models, as appropriate to the form of the secondary endpoint. The occurrence of MI, cardiac arrest, PE, stroke, cardiac composite, surgical site infection, sepsis, infection composite, awareness, persistent post-operative pain and cancer recurrence within one year post-surgery will be analysed using stratified Mantel-Haenszel Chi-square tests. Supportive analysis of these secondary endpoints will compare randomised groups using a stratified log-rank test with results summarised using Kaplan-Meier curves in which withdrawn participants will be censored at the last date they are confirmed to be event-free. Sensitivity analyses will also be undertaken for these secondary endpoints with those missing outcome data assigned a poor outcome.

ICU stay, hospital stay, days disability-free and alive within one-year post-surgery and WHODAS scores at 30 days and 1 year will be analysed using general linear models with study-centre group and randomised treatment as

fixed factors. If the data do not meet assumptions for parametric analyses, the data will be log-transformed and if this does not achieve adequate normality then the groups will be compared using the Mann-Whitney U non-parametric tests.

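### The plan has no rule for death in WHODAS or hospital stay, so the 1-year WHODAS test is survivor-only and not a randomised comparison if depth changes mortality as planned

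*Combined protocol and SAP*

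**What the plan says.** - **WHODAS.** Section 3.3 (endpoint 11) schedules WHODAS before surgery, at day 30 and at 1 year. Under section 8.2, "WHODAS scores at 30 days and 1 year will be analysed using general linear models with study-centre group and randomised treatment as" the fixed effects. If the parametric assumptions fail, the plan moves to a log transform and then to a Mann-Whitney test.
- **Missing data.** Section 12: "There will be no imputation of the ICU stay, hospital stay, days disability-free and alive within one-year post-surgery and WHODAS data at 30 days and" at one year. Its rule for using the status known at exit covers withdrawal and loss to follow-up and does not mention death. Its poor-outcome sensitivity analysis is worded for event data, and section 8.2 attaches that analysis to the listed event endpoints. Section 4.3.1 is broader, covering missing outcome data in general, but sets no poor value for a score or a length of stay.
- **Stay.** Hospital stay (endpoint 9) runs "from the start (date, time) of surgery until actual hospital discharge". Death before discharge is not addressed. ICU stay (endpoint 8) is total ICU time, first admission plus readmissions.
- **Mortality.** Section 4.2: "One year all-cause mortality is expected to be ~10"%, and "The relative risk reduction in mortality in the BIS=50 group is expected to be 20"%.
- **Endpoints that do count death.** Disability-free survival (endpoint 12) and the number of days alive and disability-free (section 8.2).
- **Multiplicity.** Section 8.2.1 applies Holm-Bonferroni to ten secondary measures without listing all ten.

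**The concern.** A patient who dies has no 1-year WHODAS. With imputation ruled out and no value assigned, that patient cannot enter the linear model. Nor does the Mann-Whitney fallback help, because the deaths are not in the ranking. The test therefore conditions on survival, which is the outcome that the trial is designed to change. If one arm keeps alive patients who would have died in the other, the two survivor groups differ in make-up, and a difference in mean WHODAS can appear although depth altered no survivor's disability. A report could then set fewer deaths against more disability, with the second half an artefact of selection.

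Hospital stay has a related gap. With no rule, a death before discharge might be dropped for want of a discharge date, or its short time in hospital might be counted as a favourable stay. That leaves an analyst's choice open until after the data are seen. ICU stay is accrued time, so a patient who dies in ICU still has a value; only the short-stay problem applies there.

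**Working it through.** **The plan's own figure.** Section 4.2: "A power analysis using $p_1=0.10$ and $p_2=0.08$ indicates that $N=3250$ patients are required in each group", with power 0.80 and alpha 0.049 (two-sided, section 8.1). The usual two-proportion formula gives 3233 per group without continuity correction and 3333 with it. Power at 3250 is 80.2%. The stated size is reproduced, so 10% (BIS 35) and 8% (BIS 50) are used below.

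**Survivors able to give a 1-year WHODAS** (no loss other than death):
- BIS 35: 3250 × 0.90 = 2925
- BIS 50: 3250 × 0.92 = 2990
- Extra BIS 50 survivors: 2990 − 2925 = 65, a share of 0.02/0.92 = 2.2%

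**Standard error of the survivor mean difference**, in SD units: √(1/2925 + 1/2990) = 0.026.

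**Shift in the BIS 50 mean.** Suppose depth has no effect on WHODAS in anyone who would survive under either target, and the extra survivors score d SD worse than the rest. The shift is (0.02/0.92) × d. With shift s in standard errors and critical value z, a two-sided test rejects with probability Φ(−z + s) + Φ(−z − s). The first Holm step is 0.05/10 = 0.005.

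| d (assumed) | Shift, SD | Shift, SE | Rejection at 5% | Rejection at 0.005 |
|---|---|---|---|---|
| 0.5 | 0.011 | 0.42 | 7.0% | 0.9% |
| 1.0 | 0.022 | 0.84 | 13.3% | 2.5% |
| 1.5 | 0.033 | 1.25 | 24.1% | 6.0% |

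At d = −0.5 (extra survivors better off) the shift is −0.011 SD, now in favour of BIS 50.

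**Day-30 WHODAS.** The documents give no 30-day mortality, so no size can be attached.

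**Hospital stay.** The documents give no in-hospital mortality either. Assume 1 to 3% in BIS 35 and the same 20% reduction:
- Extra patients alive at discharge: 3250 × 0.2 × 0.01 = 6.5, up to 3250 × 0.2 × 0.03 = 19.5
- SE: √(2/3250) = 0.025 SD
- Stay differing by 0.5 to 2 SD: shift from 0.2 × 0.01 × 0.5 = 0.001 SD to 0.2 × 0.03 × 2 = 0.012 SD, about 0.04 to 0.5 SE

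Dropping the deaths and counting them as completed stays give nearly the same size. In either case the sign depends on whether the patients saved stay longer or shorter than their comparator, which the documents do not settle.

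**The case against.** The strongest reply is that the plan already has disability endpoints that include death: disability-free survival and days alive without disability. Survivor WHODAS beside them is a defensible pair. This stands in part. Those endpoints give a reader a sound disability result, but they do not correct the separate WHODAS test, which the plan reports as a comparison of randomised groups.

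Second, the bias is small. For an assumed SD of 5 to 20 WHODAS points, 0.011 to 0.033 SD is roughly 0.05 to 0.65 points, against the 4-point individual rise that endpoint 12 calls new disability. Section 8.2 also requires mean differences with confidence intervals, so the smallness would be visible. This stands, and it limits the severity.

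Third, Holm-Bonferroni makes the nominal 5% rates too pessimistic. This stands too: 5% applies only at the last Holm step. The excess shrinks at 0.005 but remains, with 0.9 to 6.0% against an intended 0.5%.

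A reader might go further and infer that the WHODAS and stay comparisons are both necessarily biased against the arm that saves lives. The documents do not support that. For WHODAS it requires the extra survivors to be worse off than the others, which is plausible but stated nowhere. For hospital stay the direction is undetermined. Nor does ICU stay share the drop-out mechanism, given how endpoint 8 is defined.

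That the 1-year test is survivor-only is itself an inference from silence plus the bar on imputation. Even the broad wording in section 4.3.1 does not supply a score for a patient who has died.

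**Conclusion.** The concern holds as a gap in the plan with a modest consequence. No rule covers death in WHODAS or hospital stay, and the 1-year WHODAS test is in effect restricted to survivors. Under the planned 10% against 8%, it could mislead by up to about 0.03 SD (1.25 SE) over the range considered.

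This rests on assumptions outside the documents: the WHODAS gap between extra and other survivors, no loss other than death, nobody dying under BIS 50 who would have lived under BIS 35, and WHODAS being among the ten Holm measures. If depth does not change mortality, this selection effect should largely vanish.

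For hospital stay the firm point is the missing rule, not a demonstrated bias. The primary endpoint is unaffected. The change is worth making because it is cheap, not because the trial's main conclusion is at risk.

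**What to change.** In sections 8.2 and 12:

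1. Add a WHODAS comparison at day 30 and 1 year that ranks death below the worst score, using a rank test stratified by centre-group. Make it the tested analysis, or at least a pre-specified companion to it. Label survivor-only means as conditional on survival.
2. For hospital and ICU stay, state that death does not count as a favourable short stay, for example by analysing time to discharge alive with deaths ranked as the worst outcome. Use days alive and out of hospital only if hospital readmissions are collected; section 3.3 mentions readmission only for ICU.
3. Reconcile the broader poor-outcome wording in section 4.3.1 with section 12, saying which endpoints it covers and what the poor value is.

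Items 1 to 3 need SAP wording only, which section 13 allows by amendment before database lock. Mortality, WHODAS and stay are already study endpoints. The downside is that the ranked WHODAS test partly reflects mortality and gives no mean difference, so survivor means and mortality should be shown beside it.

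### WHODAS at 30 days and 1 year is compared in effect on complete cases, earlier scores go unused and no workable missing-data sensitivity analysis exists, so selective questionnaire return could bias the comparison

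*Combined protocol and SAP*

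**What the plan says.** Section 3.3, endpoint 11, schedules the WHODAS score "pre-operative, day 30 and 1 year". Section 8.2 states that "WHODAS scores at 30 days and 1 year will be analysed using general linear models with study-centre group and randomised treatment as" fixed factors. The fallback is a log transform and then a Mann-Whitney U test. Neither the pre-operative nor the day-30 score is in these models. Section 5 lists WHODAS as a baseline variable and allows adjustment in sensitivity analyses, but only if an imbalance is seen.

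Section 12 rules out filling in the score: "There will be no imputation of the ICU stay, hospital stay, days disability-free and alive within one-year post-surgery and WHODAS data", at both 30 days and 1 year.

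Missing-data sensitivity analyses appear in three places with different reach:
- Section 12 limits them to events: "Sensitivity analyses will also be undertaken with those missing outcome event data will be assigned a poor outcome".
- Section 8.2 says "Sensitivity analyses will also be undertaken for these secondary endpoints with those missing outcome data assigned a poor outcome". There, the endpoints meant are the event endpoints listed just before. WHODAS comes in the following paragraph.
- Section 4.3.1 speaks of primary and secondary outcomes and of sensitivity analyses as appropriate: "In these analyses missing outcome data will be assigned a poor outcome".

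No section says how a patient who has died enters the WHODAS score comparison.

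**The concern.** A patient with pre-operative and day-30 scores but no 1-year form drops out of the 1-year model, although the day-30 score may say a good deal about both the missing value and why it is missing. WHODAS depends on the patient, or a proxy, replying, yet it has less missing-data protection than the event endpoints. If sicker survivors reply less often and return differs by arm, the arm with poorer return will look less disabled than it is. As written, the plan neither uses the information already collected to reduce this nor tests how far the result depends on it.

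**Working it through.** **Inputs from the plan.** 3250 per group, one-year mortality 10% v 8%, power 0.8 and alpha 0.049 (Section 4.2), two-sided (Section 8.1); the WHODAS schedule and model as described. The plan gives no WHODAS SD, correlation, target difference or return rate, so there is no WHODAS figure to reproduce. The mortality sample size matters only because it fixes how many survivors could be scored.

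**1. The plan's own figure.** n = [z(α/2)·√(2p̄q̄) + z(β)·√(p₁q₁ + p₂q₂)]² / (p₁ − p₂)² = [1.9685·√0.1638 + 0.8416·√0.1636]² / 0.02² = 3233 per group. The stated 3250 is within 1% and gives power 0.802.

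**2. Survivors.** 3250 × 0.90 = 2925 and 3250 × 0.92 = 2990 could have a 1-year score before any non-return. The simulations below that use 10% or 12% v 15% non-return take 2,950 per arm.

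**3. Bias formula.** In an arm with non-return p, let Δ be the mean score of non-responders minus that of responders. The responder mean is the full mean minus pΔ. With no true difference, the complete-case contrast (arm 2 minus arm 1) is −(p₂Δ₂ − p₁Δ₁). It is zero if return is unrelated to the score, or if p and Δ match across arms. Higher WHODAS is worse, so a negative value makes arm 2 look better.

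Assume Δ ≈ 0.5 SD and non-return 10% v 15%: −(0.15 × 0.5 − 0.10 × 0.5) = −0.025 SD. Simulation gives −0.021 to −0.023. It assumes correlations of 0.5 (pre-operative/day 30), 0.4 (pre-operative/1 year) and 0.6 (day 30/1 year), a log-odds slope for non-return of 0.9 per SD, and realised non-return of 10.4% v 15.1%.

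**4. Size against the standard error.** With SE 0.0275, 0.021/0.0275 = 0.76 and 0.0227/0.0275 = 0.83. False rejection is Φ(−z + B/SE) + Φ(−z − B/SE). At 0.05 (z = 1.96) this is 12% to 13%; simulations gave about 10% to 13.5%. At 0.005, the first Holm step for ten measures (z = 2.807), it is 2.1% to 2.4%; simulation gave 2.5%.

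**5. Range for the 1-year contrast (SD units; all inputs assumed).**

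| Non-return | Return depends on | Complete-case bias | After using earlier score(s) |
|---|---|---|---|
| 10% v 15% | day-30 score | −0.021 to −0.023 | about 0 |
| 12% v 15% | day-30 score | −0.013 | about 0 |
| 10% v 15% | 1-year score | −0.037 to −0.038 | −0.024 to −0.025 |
| 10% v 20% | neither score | 0 | 0 |
| 10% v 20% | day-30 score | −0.024 to −0.033 | about 0 |
| 10% v 20% | 1-year score | −0.046 to −0.048 | −0.025 to −0.035 |
| 15% v 20% | day-30 score | −0.011 to −0.016 | about 0 |
| 15% v 20% | 1-year score | −0.023 | −0.012 to −0.018 |

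The 20% rows use a slope of 0.5 per SD and a day-30/1-year correlation of 0.5 to 0.7. In the third row, earlier scores remove (0.037 − 0.024)/0.037 = 35% of the bias.

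**6. Equal return.** With the same mechanism in both arms there is no bias, and using earlier scores loses no precision (SE 0.0276 v 0.0273 in one run, 0.0271 v 0.0267 in another). With 10% non-return in both arms but opposite mechanisms (slope 0.5, correlation 0.6), the bias is 0.059 SD. Equal return rates alone are therefore no guarantee.

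**7. Deaths.** A repeated-measures model that keeps the day-30 records of patients who later die treats their 1-year score as merely missing. With 10% v 8% mortality, all assumed after day 30 and related to the day-30 score, and equal return, it missed the survivor contrast by about 0.009 SD. The complete-case bias there was under 0.001 SD.

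**The case against.** The strongest reply is that bias needs return both to differ by arm and to relate to disability, or the mechanism itself to differ by arm. The trial blinds subjects, investigators and outcome assessors (Section 3.1), and nothing in the documents suggests unequal return. A reader might infer that the comparison *is* biased; the documents support only that it *can be*. Blinding makes differential return less likely but does not exclude it if the arms differ in true morbidity. In that case, an arm that is sicker and replies less would have a real difference shrunk rather than a false one created.

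The size is also modest. At 10% v 15% with return driven by day 30, the bias is under one standard error. Rejection of 10% to 13% applies to an unadjusted 5% test. Section 8.2.1 applies Holm-Bonferroni to ten measures; whether WHODAS is one is not stated. This stands.

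A reader might also say that the plan has no sensitivity analysis for WHODAS at all. That goes too far, because the wording of Section 4.3.1 reaches secondary outcomes. However, it fixes no poor value for a continuous score, and Section 12 bars imputation. Sections 4.3.1 and 12 also include endpoint status at withdrawal, but treating a day-30 score as the 1-year value would be carrying it forward, which the same bar excludes.

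Proxy reports may reduce loss of the sickest: "Disability will be assessed by the participant, but if unable then we will use the proxy's report". That sentence sits under disability-free survival (endpoint 12), not the WHODAS score (endpoint 11).

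Finally, the gain from earlier scores was shown for normally distributed data, whereas Section 8.2 anticipates non-normality. This stands too.

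**Conclusion.** The point holds as a conditional one. Both WHODAS comparisons are in effect complete-case, the main models ignore scores already collected, and no workable missing-data sensitivity analysis is specified. That the comparison covers only living patients is inferred from the bar on imputation; no section says so.

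Under an assumed 10% v 15% non-return, the 1-year bias is about 0.02 SD (0.8 SE) if return depends on the day-30 score, and about 0.04 SD if it depends on the 1-year score. A reader might infer that the day-30 score would correct the problem. It does so fully only in the first case and by about a third in the second, and it cannot repair its own absence. No figure here sizes the 30-day comparison; there, only the pre-operative score can help.

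Every size rests on assumed return rates, correlations and mechanisms. The point concerns one secondary endpoint and leaves the mortality primary untouched.

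**What to change.** In Section 8.2:
- Include the pre-operative WHODAS score in the analysis at both times.
- For the 1-year contrast, use the day-30 score as well, through a likelihood-based repeated-measures model or multiple imputation, with study-centre group and arm retained.
- Restrict the 1-year contrast to patients known to be alive at 1 year, so that scores are not implicitly imputed after death.
- State how deaths enter the score comparison at each time.
- Say what is done if the scores are too skewed for the chosen model.

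In Section 12:
- Remove the WHODAS scores from the no-imputation sentence.
- Reconcile that section with the poor-outcome rule in Section 4.3.1.
- Add one delta-adjusted sensitivity analysis for living non-responders, which shifts their imputed scores towards worse disability over a stated range.

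The cost is SAP wording and a little programming, with no new data or visits; Section 13 allows amendments before database lock. The downside is that the main analysis then assumes return is explained by observed scores. The delta analysis tests that assumption.
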